8.1 ALL ADVERSE EVENTS

The occurrence of all adverse event (AEs) will be documented for all subjects from the time of enrollment. Adverse Events will be categorized into three groups based on frequency: Single episode, Intermittent, or Continuous. This categorization is in lieu of other formal coding strategies (i.e., MedDRA). The final categorization of all AE's will be performed by the Sponsor but general definitions are as follows:

- Single Episode: Any AE's that occurred only once (Fall, death, etc.) as well as the first occurrence of an AE that occurs more than once.
- Intermittent: Subsequent AE's beyond the first of each type. If a subject had more than one of
 the same AE (i.e., fall), all occurrences of that AE after the first one will be included in the
 Intermittent category.

• Continuous: Any AE's that are ongoing and not resolved. Also, any AE that the subject lives with daily but doesn't result in death.

Summaries of incidence rates of individual AEs by frequency will be prepared. Because a subject may experience more than one AE per frequency, summaries will provide both the number of subjects experiencing at least one event and the number of events. Percentages provided will be the percent of subjects experiencing one or more adverse events. In addition, incidence of AEs will be presented by severity (mild, moderate, severe) and relationship to study device.

Subjects experiencing an event within a given frequency more than once will be counted under the maximum severity/relationship experienced.

A listing of all adverse events will include the subject number, date of onset, date of resolution, severity, AE type, the severity of AE, frequency of the event, the action taken, relationship to device, seriousness, and the outcome.

An additional listing will be provided that includes both site reported and adjudicated information for AEs that are adjudicated.

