8.3 Classification of AE

i. Severity of event

Each AE must be described as follows:

- the date of onset;
- date of resolution;
- severity;
- frequency of the event (single episode, intermittent, continuous);
- action taken (none, medical and/or surgical);
- relationship to study device;
- seriousness criteria must be recorded.

Each adverse event must be recorded separately.

AE Severity will be assessed using the following definitions:

Mild Aware of sign or symptom, but easily tolerated

Moderate Discomfort enough to cause interference with usual activity

Severe Incapacitating with inability to work or do usual activity

ii. Relationship to Study Agent/Product

The relationship to study device will be assessed by the site investigator using the following definitions:

Not Related Evidence exists that the adverse event definitely has a cause

other than the study device (e.g., pre-existing condition or underlying disease, intercurrent illness, or concomitant medication) and does not meet any other criteria listed.

Possibly Related

A temporal relationship exists between the event onset and administration of study device. Although the adverse event may appear unlikely to be related to the study device, it cannot be ruled out with certainty, and/or the event cannot be readily explained by the patient's clinical state or concomitant therapies.

Probably Related

A temporal relationship exists between the event onset and administration of study device and appears with some degree of certainty to be related based on known mechanism of action of the device. It cannot be readily explained by the patient's clinical state or concomitant therapies.

Definitely Related Strong evidence exists that the study device caused the adverse event. There is a temporal relationship between the event onset and administration of the study device. There is strong mechanistic evidence that the event was caused by the study device. The patient's clinical state and concomitant therapies have been ruled out as a cause.

Adverse events related to the Tango Belt could include the following:

- Discomfort, soreness, or injury due to normal wear of the belt, particularly in subjects who are very frail and thin and/or when the belt is not properly sized or fitted to the subject
- Discomfort, soreness, or injury caused by airbag deployment

iii. Adverse Event Reporting Procedures

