8.3 DEVICE RELATED ADVERSE EVENTS

Summaries of incidence rates of device related AEs by frequency will be prepared. Summaries will provide both the number of subjects and the number of events within the reporting period. Percentages provided will be the percent of subjects experiencing one or more device or procedure related adverse events. Data listings of device and procedure related AEs will also be provided, displaying details of the event(s) captured on the CRF. Relationship of the AE to the device will be judged by the investigator. Device relatedness categories include, not related, possibly related, probably related, and definitely related.

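### SAP 8.1 to 8.3 group adverse events by frequency class in place of coded terms, so no planned table is assured to give incidence by type of harm, and the single-episode row does not count single episodes

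*Combined protocol and SAP*

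**What the plan says.** **Protocol.** Section 8.3 i treats frequency as one of several attributes recorded for each event, alongside onset, severity, action taken and relationship: "frequency of the event (single episode, intermittent, continuous". It is a per-event descriptor. Section 8.3 ii names the device harms to expect: discomfort, soreness or injury from wearing the belt, or from airbag deployment. Section 8.1 makes every fall an adverse event.

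**SAP.** Section 8.1 turns the descriptor into the grouping: "Adverse Events will be categorized into three groups based on frequency: Single episode, Intermittent, or Continuous". It adds, with reference to MedDRA: "This categorization is in lieu of other formal coding strategies". It gives the final categorization to the sponsor. Single episode covers events that happened once, "as well as the first occurrence of an AE that occurs more than once". Intermittent is defined as "Subsequent AE's beyond the first of each type".

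The planned outputs are:
- All events (8.1): "Summaries of incidence rates of individual AEs by frequency will be prepared", plus incidence by severity and by relationship. A subject with repeat events within a frequency class is counted once, at the worst severity or relationship.
- Serious events (8.2): the same structure, plus a listing.
- Device-related events (8.3): "Summaries of incidence rates of device related AEs by frequency will be prepared", plus listings.
- The all-event listing carries event type. Adjudicated events and deaths also have listings.

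SAP 3.2.1 states that there is no primary safety endpoint and that safety rests on the analysis of adverse events.

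**The concern.** A safety table normally answers how many subjects had a given harm and how often. Here the place usually held by a coded term is held by a class that describes recurrence. SAP 3.1 says that the study is meant to establish safety, and the adverse-event summaries are the only analysis behind that conclusion. If they do not give a rate for belt soreness or deployment injury, a reader has to build those rates from listings, with no prespecified way of grouping terms.

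Two further features make the tables hard to interpret. The SAP redefines frequency by order of occurrence, which departs from the protocol's descriptor, and the list of changes in SAP section 9 does not mention it. The worst-case rule also works within frequency class, so it can merge events of different kinds.

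**Working it through.** The plan gives no figure to reproduce. The check applies the SAP 8.1 rules to small invented event sets and compares the two possible table layouts.

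**Rule as written.** For a subject with n events of one type (leaving ongoing events aside), single episode gains 1 event and intermittent gains n − 1.

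**Step 1: can different harms give the same table?**
- Set A: one subject with 3 falls, one with 1 fall, one with 1 skin injury.
- Set B: one subject with 3 skin injuries, two with 1 airbag soreness each.

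In both sets, single episode has 1 + 1 + 1 = 3 events in 3 subjects, and intermittent has (3 − 1) + 0 + 0 = 2 events in 1 subject.

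| Layout | Set A | Set B |
|---|---|---|
| Frequency class as the only row | Single 3 subjects/3 events; intermittent 1/2 | Single 3/3; intermittent 1/2 |
| Event type crossed with frequency | Fall: single 2/2, intermittent 1/2. Skin injury: single 1/1 | Skin injury: single 1/1, intermittent 1/2. Airbag soreness: single 2/2 |

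Under the first layout the two sets cannot be told apart. Under the second they can. The safety content of the table therefore depends on a layout that the SAP does not fix.

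**Step 2: what does the single-episode row count?**
- Ten subjects with 1 fall each: single 10 subjects/10 events; no intermittent events.
- Ten subjects with 4 falls each: single 10 subjects/10 events; intermittent 10 subjects and 10 × (4 − 1) = 30 events.

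The single-episode row is identical. For a given type it counts subjects with at least one event, not subjects with exactly one.

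**Step 3: what does the worst-case rule do?** Take one resident with mild belt soreness judged related and a severe first fall judged not related. Both are single episodes. Within that class the resident counts once, as severe, and the mild soreness no longer appears in the severity summary. If relationship is also taken at its maximum, the severity comes from the fall and the relationship from the soreness. Applied within event type, the rule would keep the two apart.

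**Step 4: which layout does the text favour?**
- For type crossed with frequency: 8.1 and 8.2 refer to individual events, and the intermittent rule needs events to be identified by type.
- For frequency class as the counting unit: 8.1 offers the classes as a substitute for coding; it explains the double count by saying that a subject can have several events in one frequency class; its worst-case rule works within that class; and 8.3, the device-related summary, drops the word individual.

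The SAP abbreviation list defines preferred term and system organ class, but section 8 uses neither.

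**The case against.** The strongest reply is that the text allows a sound table. Individual events by frequency can mean each event type split by frequency class. On that layout nothing is lost: for falls, the intermittent subject count is the number of recurrent fallers, and the single-episode count is the number with at least one fall. The listings carry type, severity, relationship, seriousness and outcome. With 134 to 268 belt subjects planned (SAP section 4), harms could be counted by hand. Relationship is judged by the investigator, so the sponsor's final say covers only the frequency class. Falls judged unrelated to the belt drop out of the device-related summary, and fall occurrence, major injuries due to fall and airbag deployment are separate ancillary endpoints.

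All of this stands, and it rules out some stronger readings. A reader might infer that the outputs cannot show which harms occurred, that deaths, falls and skin injuries must share one row, or that recurrent fallers go uncounted. The documents do not support these. The listings identify harms, no table shell fixes a pooled row, and the recurrent-faller count survives if rows are split by type.

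The reply does not show that a table by type is planned. The counting language in 8.1 and the wording of 8.3 point the other way. Listings give cases rather than prespecified rates, and two programmers could build different safety tables from the same text.

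**Conclusion.** The point holds as a minor one about reporting. SAP 8.1 to 8.3 put frequency class where a coded term would normally stand and collapse repeat events within that class. Harms can be found case by case, but no planned table is assured to give incidence by type of harm. The single-episode label misleads under either layout, because a subject with recurrent events is counted there as well as under intermittent.

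No numerical size can be given: the documents contain no adverse-event rates, and the examples above are invented to show how the rules behave. The conclusion rests on the SAP text alone. Table shells and the case report form are not in the documents, and shells that already split rows by type would answer the main part of the point. The effectiveness analyses are not affected.

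**What to change.** Revise SAP 8.1 to 8.3 as follows:
- Tabulate all, serious and device-related adverse events by event type, giving subjects and events, severity and relationship.
- Apply the worst severity or relationship rule within event type rather than within frequency class.
- Show falls on their own line.
- Keep frequency as the per-event descriptor recorded under Protocol 8.3 i, and reserve single episode for events that did not recur.

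Event type is already a field in the planned listing, so the cost is a few more tables. If that field is free text, which the documents do not say, the terms would also need consistent grouping before they are tabulated.

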8.2 Serious Adverse Events

Summaries of incidence rates and relationship to the investigational device of individual Serious Adverse Events (SAEs) by frequency will be prepared. Summaries will provide both the number of subjects and the number of events within the reporting period. Percentages provided will be the percent of subjects experiencing one or more serious adverse events. A data listing of SAEs will also be provided, displaying details of the event(s) captured on the CRF.

8.3 DEVICE RELATED ADVERSE EVENTS

Summaries of incidence rates of device related AEs by frequency will be prepared. Summaries will provide both the number of subjects and the number of events within the reporting period. Percentages provided will be the percent of subjects experiencing one or more device or procedure related adverse events. Data listings of device and procedure related AEs will also be provided, displaying details of the event(s) captured on the CRF. Relationship of the AE to the device will be judged by the investigator. Device relatedness categories include, not related, possibly related, probably related, and definitely related.

8.4 DEATHS

Should any subjects die during the course of the trial, relevant information will be supplied in a data listing.

9 SUMMARY OF CHANGES FROM THE PROTOCOL

The following table provides a list of changes from the protocol to the SAP, and the justification for each change.

Section	Description	Justification
4. Sample Size	Estimated attrition was changed from	After roughly half the subjects in the
	20% to 30%	Tango Belt group were exited, the
		attrition rate was reexamined and
		adjusted upwards to account for the
		higher-than-expected loss.
4. Sample Size	Historical Control rate of major hip	The sample size estimate was revisited
	injury estimate changed from 8% to	after it was clear that the expected 1:4
	15%	allocation ratio was not attainable. The
		HC rate of major hip injury was also
		examined and deemed to be much higher
		than estimated at the beginning of the
		trial.

10 REPORTING CONVENTIONS

All reporting will meet the standards of SOP-68 AS Data Analysis Reporting and SOP-83 AS Programming Standards.

